9.5.2 BASELINE EXAMS, TESTS AND QUESTIONNAIRES

After the subject has signed the informed consent form and agreed to participate in the study, the exams, tests and questionnaires listed in the Baseline column of Table 3 should be performed. Refer to Appendix A for instructions for performing the exams and administering the questionnaires.

At this visit, subjects should undergo the following tests and exams, performed in the order indicated below, to screen them for the study qualification and to record baseline data. Items with an asterisk (*) must be performed by a Masked Assessor (Refer to Section 9.7 for more information on the Masked Assessor).

1. Questionnaires: OSDI, SANDE and Eye Dryness VAS
2. Demographics, medical and ocular history
3. Medication use: ocular and systemic

4. Manifest refraction and ETDRS Best-corrected visual acuity*
5. Slit Lamp Exam*
6. Tear Breakup Time*
7. Corneal Staining*
8. Conjunctival Staining*
9. Schirmer 1 Test
10. Meibomian Gland Secretion Scoring*
11. Intraocular pressure*

If, at any point during the visit the subjects fails to meet a subject selection criterion, then the visit can be terminated. Subjects who fail to meet all the selection criteria will be considered a screen failure and will be withdrawn from the study.

Subjects who fail screening may be re-screened for the study after 60 days. If they are re-enrolled, they should be assigned a new subject ID.

NOTE: Questionnaires and exam data collected on subjects prior to enrollment as part of the routine clinical practice may be used to pre-screen patients for the study. However, once the subject signs the consent form and is enrolled in the study, these questionnaires and exams must be repeated following the protocol procedures.

After all required measurements have been obtained and it has been confirmed that the subject meets all the Subject Selection Criteria, then the subject will be Randomized.

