9 STUDY PROCEDURES

9.1 STUDY SCHEDULE

Table 3: Study Visit Schedule

Visit (Visit Window)	Baseline (Day -7 to 0)	Treatment ^b (Day 0)	Day 1 (Day 1)	Week 2 (Day 12-16)	1 Mo (Day 21 – 35)
Informed Consent	X ^a				
Demographics, Ocular & Medical History	X				
Medication use	X			X	X
Questionnaires: OSDI, SANDE, Eye Dryness Score	X				X
Manifest Refraction and Best-corrected visual acuity (ETDRS)	X		X ^c	X ^c	X
Slit Lamp Exam	X		X	X	X
Tear Breakup Time	X			X	X
Corneal Staining	X			X	X
Conjunctival Staining	X			X	X
Schirmer 1 Test (without anesthesia)	X				
Meibomian Gland Secretion Scoring	X			X	X
IOP^d	X		X	X	X
Subject Eligibility	X				
Randomization	X				
TearCare or LipiFlow Treatment		X			
AE Assessment	X	X	X	X	X
Discomfort/Pain Questionnaire		X	X		
Collect Eye Drop/Lubricant Log					X

^a Subjects may sign the informed consent up to 30 days in advance of the baseline visit.

^b The TearCare or LipiFlow treatment must be performed within 7 calendar days of the Baseline visit. If scheduling permits, it may be performed on the same day as the Baseline visit following Randomization. Refer to Section 9.5.1 for details.

^c On Day 1 and Week 2, Best Corrected Spectacle Visual Acuity (BCSVA using EDTRS) is measured without manifest refraction (MR). If the VA has worsened by ≥ 10 letters (per ETDRS) from baseline, then MR should be performed, the ETDRS measurement should be repeated, and the VA post-MR should be recorded.

^d IOP measured via applanation tonometry should be measured at baseline using standard of practice at each site with the same method to be used for all consecutive visits in the study.

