9.5 BASELINE AND TREATMENT VISIT(S)

9.5.1 SCHEDULING THE BASELINE AND TREATMENT VISIT(S)

To facilitate scheduling, the Baseline and Treatment Visits may be performed in the same day or on two separate days. If these visits are performed over two days, the Treatment Visit must be within 7 calendar days of the Baseline Visit. For follow-up scheduling purposes, the date of the Treatment Visit is Day 0.

Refer to Table 3 for which tests and exams are to be performed in each visit. Endpoint assessments performed during the Baseline visit must be performed by a Masked Assessor (See Section 9.7).

Since dry eye drops and lubricants can affect the endpoint assessments, instruct subjects not to use any of these products within 2 hours of the Baseline visit.

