9.10 WITHDRAWAL AND DISCONTINUATION

All subjects have the right to withdraw at any point during the treatment without prejudice. The investigator can discontinue any subject at any time if continued participation in the study would result in harm to the subject. All efforts should be made by the investigator to retain the subject in the study. If a subject withdraws prematurely from the study, a genuine effort must be made to determine the reason(s) the subject discontinued the study. The reason must be recorded in the subject’s file and on the Study Exit Form.

If a subject withdraws from the study post-randomization but prior to receiving the TearCare or Warm Compress treatment, then that subject may be replaced in the study by a newly enrolled subject.

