12.2 ANALYSIS POPULATIONS

The per-protocol analysis population includes all subjects who have at least one follow-up visit and have no major protocol deviations, including specifically no use of dry-eye medications (Xiidra, Restasis). The primary and secondary endpoint analysis will be performed based on the Cohort 2 per-protocol population.

The intent-to-treat (ITT) analysis population includes all subjects who are randomized to either arm, regardless of treatment received. As a sensitivity analysis, the primary and secondary endpoint analyses will also be carried out on the Cohort 2 ITT population as well.

The effectiveness outcomes for Cohort 1 subjects will be summarized descriptively based on the available data of the per-protocol population. The effectiveness data listings will be Cohort 1 subjects that are excluded from in the per-protocol population will be provided separately.

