16 DEVICE FAILURES AND MALFUNCTIONS

All device failures or malfunctions should be recorded on the Device Deficiency Form and reported to Sight Sciences Customer Service [REDACTED]).

If the TearCare or LipiFlow procedure cannot be completed due to a product failure or malfunction, the procedure may be rescheduled for a different day. Every effort should be made to reschedule the procedure within the next 7 calendar days of the Baseline visit.

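### For subjects treated on a later day, randomization at Baseline leaves up to 7 days in which an unmasked subject can learn the arm, leave and be replaced, with no scheduled re-check of eligibility before treatment

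*Combined protocol and SAP*

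**What the plan says.** Table 3 (Section 9.1) marks the Subject Eligibility and Randomization rows once each, in the Baseline column, whose window is Day -7 to Day 0. Section 9.5.2 gives the same order: after the measurements are done and "it has been confirmed that the subject meets all the Subject Selection Criteria, then the subject will be Randomized". Section 9.5.1 sets the gap: "If these visits are performed over two days, the Treatment Visit must be within 7 calendar days of the Baseline Visit". Same-day treatment is optional, and note b to Table 3 still places it after allocation: "If scheduling permits, it may be performed on the same day as the Baseline visit following Randomization". After a device failure, Section 16 softens the limit: "Every effort should be made to reschedule the procedure within the next 7 calendar days of the Baseline visit".

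The Treatment column of Table 3 holds the procedure, adverse event assessment and the Discomfort/Pain Questionnaire. The step lists in Sections 9.5.4 and 9.5.5 contain no eligibility step. Section 9.5.3 supplies assignments to the site in envelopes and does not say that the arm is withheld until the treatment day. Section 7 states that subjects are not masked.

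Section 9.10 permits replacement of a subject who "withdraws from the study post-randomization but prior to receiving the TearCare or Warm Compress treatment". Section 12.2 defines the deciding set: "The per-protocol analysis population includes all subjects who have at least one follow-up visit and have no major protocol deviations". The ITT set, used for sensitivity analysis, keeps everyone randomized.

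**The concern.** Two things can happen between allocation and treatment. First, a subject who learns the arm, and who may prefer the other one, can withdraw before Day 0. A withdrawal of that kind depends on the arm, and filling the place with a new subject restores the count of treated subjects but not the randomized comparison. Second, a subject's status against the selection criteria can change, and no visit procedure asks about it before treatment. Several continuing restrictions (the barred medications in exclusion 1 and contact lens wear in exclusion 4) are worded for the 1-month follow-up, which counts from Day 0, and medication use is next recorded at Week 2.

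At stake is the false-positive rate of the non-inferiority conclusion. The per-protocol analysis decides the trial, and a subject with no follow-up visit is not in it.

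**Working it through.** **1. The plan's own figure.** The inputs are in SAP Sections 22.3.1 and 22.3.2: one-sided alpha 0.05, 95% power, true difference 0, 10% loss, two eyes per subject. Eyes per group: n = 2(1.645 + 1.645)² × SD² / margin².

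- TBUT (SD 6.0, margin 3.0, design effect 1.4): 2 × 10.82 × 36/9 = 86.6, so 87 by the normal formula and 88 by the t-test. Then 176 × 1.4 = 246; 246/0.9 gives 274 eyes, or 137 subjects.
- MEIB (SD 9.0, margin 5.0, design effect 1.5): 2 × 10.82 × 81/25 = 70.1, so 71. Then 142 × 1.5 = 213; 213/0.9 gives 237 eyes, or 119 subjects.

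Both reproduce. Nothing in this point changes an input, so N stays at 138.

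**2. What happens to a subject who leaves before Day 0.**

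- *Per-protocol:* excluded, because there is no follow-up visit.
- *ITT:* included by definition, but with no Week 2 or Month 1 value. The mixed model in Section 22.1.1 is fitted to the 1-month change, so without imputation this subject contributes nothing to it.
- *Multiple imputation (Sections 12.5.5 and 22.1.3):* the SAP expects the 2-week result to be the strong predictor, and this subject has none. Only baseline data remain. Section 22.1.3 details the method for TBUT only.

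**3. Possible shift (assumed; no loss rate is given).** If a fraction f of one arm leaves and would have differed from the stayers by k SD, the observed mean of that arm moves by f × k × SD.

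| f (of 69 per arm) | k | TBUT shift, s | MEIB shift, units |
|---|---|---|---|
| 2% (1.4 subjects) | 0.25 | 0.03 | 0.04 |
| 5% (3.5) | 0.5 | 0.15 | 0.23 |
| 5% (3.5) | 1 | 0.30 | 0.45 |
| 10% (6.9) | 1 | 0.60 | 0.90 |

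**4. Effect on error at the margin.** With 138 × 0.9, about 124 evaluable subjects, there are 124 eyes per arm. Dividing by the design effect gives 124/1.4 = 88.6 effective eyes per arm for TBUT and 124/1.5 = 82.7 for MEIB. The standard errors are 6 × √(2/88.6) = 0.90 s and 9 × √(2/82.7) = 1.40 units. For a shift b favouring TearCare, the one-sided error for that endpoint is Φ(b/SE − 1.645).

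- TBUT: b = 0.15, 0.3, 0.6 s gives 0.070, 0.095, 0.164.
- MEIB: b = 0.225, 0.45, 0.9 units gives 0.069, 0.093, 0.158.

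**5. Replacement.** If 2%, 5% or 10% left before treatment and were replaced until 138 had been treated, 138/(1 − w) gives 141, 146 or 154 randomized. The treated count is restored; the selection remains.

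**The case against.** The protocol gives a scheduling reason for allowing two days, and same-day subjects are not exposed at all; the share treated on a separate day is not stated. Both points stand.

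A reader might infer that subjects are told their arm at Baseline and that any losses are therefore arm-driven. The documents do not say so. Section 7 explains the lack of masking by what subjects see when treated. The plan fails to prevent disclosure; it does not require it.

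A reader might also infer that early leavers would use up part of the 10% loss allowance. That does not fit Section 9.10: a replaced subject costs the allowance nothing. The issue is selection, not sample size.

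There is partial protection. Section 12.3 requires accounting for dropouts with reasons, ITT with imputation retains baseline information, and the baseline covariate would absorb any difference explained by the baseline value. On the treatment day adverse events are assessed. Section 11.6 puts TearCare treatments under the investigator's supervision, Section 9.10 lets the investigator discontinue a subject to avoid harm, and Section 18.3.2 makes the investigator responsible for conformity with the criteria. These narrow the gap, but none is a scheduled re-confirmation of eligibility, and Section 10.1 defines an adverse event for a subject already treated.

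Finally, Section 9.10 could be read literally to mean that a LipiFlow subject, who receives neither named treatment, may be replaced at any time. Sections 12.1 and 16 both name TearCare and LipiFlow, so this is a carry-over slip that needs correcting and adds no weight to the point.

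**Conclusion.** The point holds as a weakness of design for subjects treated on a separate day: allocation precedes treatment by up to 7 calendar days (Section 16 makes that a best-effort target after a device failure), concealment over that interval is not required, eligibility is not re-confirmed on schedule, and leavers may be replaced. Neither planned analysis set has follow-up data for them.

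The size cannot be derived from the documents. Under the assumed ranges every shift lies well inside the margins. The error of about 0.07 corresponds to 5% loss from one arm with a 0.5 SD difference; the 0.16 needs 10% loss from one arm and a full 1 SD difference. These figures apply per endpoint, ignore the baseline covariate, and assume that the shift favours TearCare; the direction is unknown and could be the reverse. This is a cheap improvement worth making, not evidence that the result would be biased.

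**What to change.** - In Table 3 and Sections 9.5.2 and 9.5.3, move Randomization to the treatment visit, immediately before the procedure. Open the envelope only after site staff document that the protocol's existing selection criteria are still met. Same-day Baseline and treatment remains possible.
- In Section 9.10, either limit replacement to subjects not yet randomized, or state that every randomized subject stays in ITT and report losses between randomization and treatment by arm.
- Reconcile the warm compress wording in Section 9.10 with the LipiFlow control.

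Cost: protocol wording and a short documented check, with no added visit, test or subject. Both devices must be ready on Day 0 because the arm is not known in advance; Section 9.3 already lists both as site equipment.

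A reader might infer that this removes the loss altogether or closes every safety gap. It does neither. A subject can still refuse once the envelope is opened, rescheduling under Section 16 can reopen the interval, and a brief check by history or external look could miss a condition that needs the Baseline slit-lamp and staining examinations, such as a corneal epithelial defect.

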9.5.3 RANDOMIZATION

Subjects will be randomized to either the TearCare (i.e. “treatment group”) or LipiFlow (i.e. “control group”) using a pseudo-random number generator with subjects enrolled according to a predetermined list. Randomization will use permuted blocks with random block sizes of 2 or 4. The investigational site will be provided a set of envelopes with randomization assignments. Following randomization, the subject should undergo the applicable procedures described in the sections below.

9.5.4 TREATMENT FOR TEARCARE GROUP

Subjects randomized to the TearCare Group will undergo the following procedure bilaterally. Refer to the TearCare Instructions for Use for detailed instructions for operating the TearCare System.

1. Obtain a new set of SmartLid devices and a TearCare SmartHub with enough battery left for at least one procedure.
2. Wipe the subject’s eyelids and temple with the makeup removal wipe provided by the Sponsor. Allow the skin to dry or pad dry with a tissue. Use care not to allow any of the wipe to get into the eye.

3. Place a pair of SmartLid devices on the subject's eyelids and affix the temple housing to the subject's temple. Use the clip to secure the cables behind the subject's head.
4. Connect the SmartLid devices to the SmartHub.
5. Inform the subject that the SmartLid devices will heat up very quickly once the TearCare procedure is started.
6. Start TearCare procedure. Subjects should be encouraged keep their eyes open and blink naturally during the TearCare procedure.
7. If the subject indicates the temperature is too hot, decrease the temperature set point to a setting that is comfortable for the subject.
8. Following the thermal portion of the TearCare treatment, remove the SmartLid devices from the subject and position the subject at the slit lamp to perform expression of the meibomian glands. Begin performing expression within 3 minutes of completion of the thermal portion of the procedure.
9. Apply 1 drop of proparacaine or tetracaine into each eye.
10. Using the Clearance Assistant Device, express the meibomian glands in all 4 eyelids using the following technique:
 - a. Think of each eyelid as having 3 zones: nasal, central & temporal.
 - b. For each zone, start at the fornix and work your way up to the margin.
 - c. Position the forceps horizontal, parallel to the margin.
 - d. Apply moderate continuous pressure and adjust based on the gland output.
 - e. Perform a second pass on the same eyelid to further express the glands.
 - f. After treating the lower and upper eyelids, repeat expression on all 4 lids to ensure complete expression. Additional passes of expression may be performed to ensure complete expression.
 - g. Should the subject experience discomfort, it is reasonable to apply additional topical anesthetic (i.e. proparacaine or tetracaine). Alternatively, Akten® (lidocaine hydrochloride ophthalmic gel) 3.5% or equivalent may be applied into the lower eyelid fornices.
 - h. The goal is to express each zone until the meibum coming out is clear. Typically, complete expression takes approximately 5 minutes/eye.
11. Immediately following the treatment, ask the subject to complete the Pain/Discomfort Questionnaires.

9.5.5 TREATMENT FOR LIPIFLOW GROUP

Subjects randomized to the LipiFlow Group will undergo the following procedure bilaterally. Refer to the LipiFlow Instructions for Use for detailed instructions for performing the LipiFlow procedure.

1. Seat the subject in a reclining chair.
2. Place an anesthetic drop in each eye.

3. Put a lubricating drop on the surface of the sterile, disposable Activator.
4. With a finger placed on the lid between the lid margin and the orbital bone, roll the finger to lift the lid margin of that particular lid off the globe.
5. Have the subject look down at their feet and slip the Activator below the upper lid of the first eye.
6. Have the subject then look up and place the Activator behind the lower lid. Have the subject close their eyes.
7. Align the handle of the Activator so that it is parallel to the bridge of the subject's nose. Place a piece of tape to secure the handle to the bridge of the subject's nose.
8. Assure that the outer surface so the bladder comes in full contact with the external side of the lids.
9. Loop the tubing over the subject's ear.
10. Repeat for the fellow eye.
11. Plug the tubing into the LipiFlow console.
12. Initiate the procedure by pressing start button on the console.
13. The procedure will last 12 minutes.
14. Once the procedure is complete, remove the tape from one Activator. Slightly depressed the sclera to release any suction between the disposable and the eye.
15. Have the subject look up and slip the Activator from under the lower lid, and then look down and remove from the upper lid.
16. Repeat for the fellow eye.
17. Place a lipid based drop in each eye.
18. Immediately following the treatment, ask the subject to complete the Pain/Discomfort Questionnaires.

9.5.6 FOLLOW-UP INSTRUCTIONS FOR SUBJECTS

Review the following instructions with subjects at the completion of the visit.

During the 1 month follow-up:

1. Dry Eye Lubricants/Drops: Subjects should make every effort to refrain from using any dry eye drops, lubricants, or other type of dry eye treatment (e.g. warm compresses, prescription medication, etc.). If they require “rescue therapy” to relieve their symptoms, they should use the same type of drops or lubricants they were using prior to the study.
2. Dry Eye Lubricant/Drop Log: Provide subjects with the Lubricant/Drop log and instruct them to record any use of drops or lubricants during the follow-up period.
3. Other Dry Eye Medications: Subjects should not use any other medications for dry eye disease (e.g. Restasis, Xiidra, etc.)
4. Other Treatments for Dry Eyes: Subject should not have any other treatments for dry eyes. For example, they should not use warm compresses or perform lid

massage. They should not use the True Tear device or have any other in-office dry eye treatments.

5. Anti-histamines: Subjects should not use any anti-histamines.

9.6 FOLLOW-UP VISITS

Prior to the Visit: Reminder Call

A few days before the follow-up visit, it is recommended that the coordinator contact the subject to remind them not to use dry eye drops or lubricants on the day of the follow-up visit since these products can affect the endpoint assessments.

At the Beginning of the Follow-up Visit: Maintaining Masking of Study Personnel

Endpoint assessments performed during the Follow-up visit must be performed by the Masked Assessor (See Section 9.7).

At the beginning of the follow-up visit, the coordinator should remind the subject to not reveal their randomization group to the study personnel who will be performing the follow-up exams.

Order of Procedures During the Follow-Up Visit

Follow-up procedures will be performed per the Study Schedule provided in Table 3 (page 30) and the methods included in Appendix A. Since certain tests/exams can impact the ability to perform other tests/exams, the following tests and exams should be performed in this order:

1. Questionnaires
2. Manifest refraction, if required per this protocol, and ETDRS Best-corrected visual acuity
3. Slit Lamp Exam
4. Tear Breakup Time
5. Corneal staining
6. Conjunctival staining
7. Meibomian Gland Secretion Scoring
8. IOP
9. Assessment of adverse events

The following activities can be performed in any order:

- Medication Use
- Collection of Lubricant/Drop Log (for the 1 Month visit only)

9.7 PHOTOGRAPHY DURING EXAMS AND TEARCARE PROCEDURE

Photographs or videos may be made during the baseline or follow-up exams or during the TearCare procedure. These images may be used for educational, training or marketing purposes. Subject consent must be obtained prior to taking any photographs or videos. Subjects do not have to agree to consent to being filmed in order to participate in the study.

9.8 MASKED ASSESSOR

To reduce potential bias in the study, study staff performing endpoint assessments will be masked as to the subject's treatment arm. In addition, to ensure consistency in performing the endpoint assessments the study staff member who performs the baseline assessments should also perform the follow-up assessments. An alternate Masked Assessor may be appointed to handle scheduling conflicts, but every effort should be made to have the same person performing all endpoint assessments throughout the study. Masked Assessors may not perform the randomization, the TearCare procedure, or the Lipiflow procedure

The following assessments must be performed by a Masked Assessor:

- Manifest refraction and BCVA
- Slit lamp exam
- Tear Break-up Time
- Corneal staining
- Conjunctival staining
- Meibomian gland secretion scoring
- IOP
- AE assessment

